7.0 Interim Analyses

While the study is in progress, a Data Monitoring Committee (DMC) will conduct planned reviews of the study data to evaluate the safety, tolerability and activity of the study drug treatment. Detailed information can be found in the DMC Charter and Data Monitoring Analysis Plan.

An interim analysis will also be conducted when all subjects in Cohorts 1 and 2 have completed their Week 24 visit. This interim analysis will only include Cohort 1 and 2 efficacy and pharmacodynamic data till Week 24. All safety data from Cohorts 1 and 2 will be presented, though the key data for the interim analysis will be data reported till Week 24. The tables generated for the interim analysis are identified in the list of TFLs.

The main clinical study report (CSR) will be written when all subjects in Cohorts 1 and 2 have completed their Week 48 visit. This CSR will include all available data from these two cohorts (including extension data) and serious adverse event data from Cohort 3.

Further analyses will be conducted when all subjects in Cohort 3 have completed their Week 48 visit and prior to submission. The final reporting of data from this study will be conducted at the end of the study (when SMT C1100 is either approved in the relevant countries or development of SMT C1100 is discontinued).

8.0 Data Review

8.1 Data Handling and Transfer

Data will be entered into a Medidata Rave database and exported as SAS[®] version 9.4 datasets. Converted datasets will be created using SAS and following standard Clinical Data Interchange Standards Consortium Standard Data Tabulation Model (CDISC SDTM, version 1.3, Implementation Guide version v3.1.3) conventions. Analysis datasets will be created using SAS and following CDISC Analysis Data Model (ADaM, version 2.1, Implementation Guide 1.0) standards.

Medical history and AEs will be coded using the Medical Dictionary for Regulatory Activities (MedDRA), version 19.0 on an ongoing basis to assign a system organ class (SOC) and preferred term (PT) to each event. Prior and concomitant medications and steroids will be coded using the World Health Organization Drug Dictionary WHO DDE B2 Dec_2015 (Enhanced) on an ongoing basis.

Additional details can be found in the PRA Coding Conventions and the Data Management Plan for this study.

8.2 Data Screening

In addition to the data cleaning described in the Data Management Plan, the programming of analysis datasets, tables, figures, and listings (TFLs) will include additional data reviews when data are extracted for reporting (e.g. DMC meetings and preparation of patient profiles). Presumed data issues will be extracted into SAS logs identified by the word “Problem” and extracted from the logs by a SAS macro and sent to Data Management.

Review of a pre-freeze TFL run and a post-freeze TFL run on the frozen database will allow for further data reviews prior to database lock. The post-freeze TFLs will be discussed with the sponsor in a data review meeting to identify any final data issues and seek corrections prior to database lock. The PRA statistician and the sponsor must approve the database lock.

A similar process will be followed for the different analyses described in [Section 7](#), except on these occasions the database will only be frozen and not locked.

9.0 Statistical Methods

9.1 General

All statistical analyses will be performed using SAS (Version 9.4).

Unless otherwise specified, descriptive data summaries will be tabulated for all endpoints. Categorical data will be summarized using number of subjects (n), frequency and percentages of subjects falling into each category, with the denominator for percentages being the number of subjects in the study population, unless otherwise noted. Percentages will be rounded to one decimal place except for 100%, which will have no decimal place. Counts of zero will not display a percentage.

All continuous variables will be summarized using mean, standard deviation, median, Q1, Q3, minimum, maximum, and number of subjects with observations. The mean, median will be presented to one decimal place greater than the original data, standard deviation will be to two decimal places greater than the original data, and the minimum and maximum will have the same number of decimal places as the original data.

For both categorical and continuous variables the number of missing values will be presented in summary tables and will be split by the number of missing values due to discontinuation of treatment and due to missing. Subjects will only be counted if they had the potential to reach the visit (e.g. a subject who has been in the study 48 weeks will not be considered as having a missing Week 60 visit). Their potential to reach a visit is based on the duration of time they could have been in the study, from their first dosing date till the datacut date. If a subject does not have a record for a visit and did not discontinue treatment, then the record will be counted as due to missing. For subjects who discontinue treatment then the date of discontinuation will be considered as the date of the last dose of study medication plus 1 day, any missing records prior to this date will be classed as missing and any missing records after this date will be

classed as discontinued. The target study day for a visit will be used to assess whether a subject could have had a visit prior to discontinuation of treatment.

Section 5 provides details of where efficacy data is imputed if the reason given for not performing or completing an assessment is related to the subject's medical condition (e.g. if a subject is physically unable to do the 6MWD then their distance will be imputed as 0). For such efficacy endpoints the number of imputed values will also be tabulated along with other descriptive statistics in summary tables.

Listings will present cohort as a sub-header. Unless otherwise specified, tabulations will present data for each cohort separately as well as all subjects.

In by-time summary tables the baseline will be summarized using all available data, but also for each visit using only the baseline data from subjects with available data at the visit; hence the mean change from baseline will equal the mean visit value – mean baseline value.

All data will be listed and will present study days in addition to dates. Dates will be presented in DDMMYY format (e.g. 28Jul2017).

Listings will be sorted by cohort (used as sub-header), subject and, where appropriate, time.

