6.2 Intention-to-Treat Population

The Intent-to-Treat (ITT) population is defined as all subjects who received at least one dose of study medication.

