6.4 Endpoint Populations

Separate populations will be identified for different sets of endpoints, based upon their baseline ability to be assessed for the relevant endpoints. These populations will be:

- Leg MRI/MRS Population (*Cohorts 1 and 2*)
- Cardiac MRI Population (*Cohort 3*)
- Biopsy Population
- Functional measures Population
- Blood Biomarker Population
- PK Population

All subjects in the ITT population will be included in each set if they also have at least one assessment of an endpoint in the set (which could be their baseline assessment).

Justification for exclusions from populations will be documented prior to reporting.

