9.1.1 Methods for Handling Dropouts and Missing Data

Imputation details concerning missing efficacy data where a subject has attended the relevant visit are discussed in **Section 5**. Where missing data is due to a missed visit values will not be imputed.

The imputation approaches for handling partial or missing start and/or end dates of AEs and concomitant medications are summarized in **Appendix 2**. Partial and missing AE or concomitant medication dates will be imputed with conservatism. Unless an AE is proven to occur prior to the first dose of the study drug, it will be considered to be a treatment-emergent adverse event (TEAE). Similarly, a medication with a missing stop date will be considered as concomitant medication unless there is obvious evidence that the stop date is prior to the first date of IMP treatment. If the day, or month and day, of the start date are not obviously before the date of first IMP treatment, then the start date will be imputed as the first day of the available month and or year, or the start date of IMP, whichever is later.

The imputed dates will be used to assess whether AEs should be considered to be treatment emergent, medications should be included in the safety summaries as prior and/or concomitant, and for the calculation of AE durations; however, the original partial/missing dates will be included in data listings.

Partial dates for age at diagnosis will also have the missing information imputed for the purposes of calculating the duration since diagnosis. The earliest date consistent with the information provided will be used.

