The potential for a subject to have reached a visit will be determined by calculating the duration between the data cut date and the subject's first dose date (*i.e. data cut date – first dose date + 1*), regardless of whether they withdraw from the study. If this duration is longer than the target study day for a visit, then the subject will be deemed to have had the potential to reach the visit. A check will also be made for subject's attending a visit earlier than the visit target day; if this is the case the subject will be included in the count of potential subjects.

For example, consider a data cut date of 1st December 2016

Subject X: has their first dose on 15th June 2016: the data cut date would be the subject's Study Day 170. Hence the subject could have reached the Week 24 visit (168 days).

Subject Y: has their first dose on 25th June 2016: the data cut date would be the subject's Study Day 160. Hence the subject was not scheduled to have reached the Week 24 visit. However, if they attended their Week 24 visit early (*e.g. Day 158*) they would be counted.

For percentages the number of subjects in the ITT/Safety populations will be used as the denominator.

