9.6.3 North Star Ambulatory Assessment

Scores and changes from baseline will be summarized by visit using descriptive statistics for both the total score and the linearized score.

The individual activity scores will be summarized by visit using a shift table from baseline. Marginal totals will be included.

The number (percentage) of subjects who have lost 0, 1, 2...activities will be tabulated by visit.

The velocities of change for the total score will be summarized using descriptive statistics. Velocities of change will also be analyzed using the methods described in [Section 9.6.1](#).

The 6MWD and NSAA total score changes from baseline will be plotted together against visit in trellis plots with one subject per plot. The two parameters will have different y-axes and a legend will be provided to distinguish 6MWD and NSAA lines on the plot.

Individual subject total scores will be plotted against age as individual line plots (spaghetti plots).

Week 12, 24, 36 and 48 changes from baseline for the total scores will also be plotted against age on Day 1 and baseline, using different symbols to identify the Week. The Pearson correlation coefficient (for each week) will be footnoted on the plots.

The box and whisker and mean change from baseline plots will only be presented for the total scores.

The number and percentage of subjects who lose ambulation will be summarized by visit.

9.6.4 10-Metre Run/Walk

Scores and changes from baseline will be summarized by visit using descriptive statistics.

The velocities of change will be summarized using descriptive statistics. Velocities of change will also be analyzed using the methods described in [Section 9.6.1](#).

Individual subject data will be plotted against age as individual line plots (spaghetti plots).

Week 12, 24, 36 and Week 48 changes from baseline will also be plotted against age on Day 1 and baseline, using different symbols to identify the Week. The Pearson correlation coefficient (for each week) will be footnoted on the plots.

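### By-visit percentages are divided by the whole analysis population, so they shrink at split ECG time points and at extension visits that not every boy has reached

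*SAP*

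**What the plan says.** SAP 9.1 gives the general rule for categorical summaries, "with the denominator for percentages being the number of subjects in the study population, unless otherwise noted".

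The by-visit categorical tables do not depart from it. They are: orthoses or aids and falls or support (9.6.2); NSAA activities lost and loss of ambulation (9.6.3, for example "The number and percentage of subjects who lose ambulation will be summarized by visit"); MRS fat-fraction shift tables (9.7.1); ECG interpretation by visit and time point (9.8.5); echocardiogram (9.8.6); and physical examination (9.8.7).

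The populations are wide. On ITT: "The Intent-to-Treat (ITT) population is defined as all subjects who received at least one dose of study medication". The Safety population has the same definition. The endpoint populations in 6.4 take ITT subjects "if they also have at least one assessment of an endpoint in the set (which could be their baseline assessment").

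For missing-value counts, 9.1 uses a narrower rule: "Subjects will only be counted if they had the potential to reach the visit". SAP 9.2 works out that potential for every scheduled visit and prints it, but then says: "For percentages the number of subjects in the ITT/Safety populations will be used as the denominator".

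Two further provisions bear on the size. SAP 9.1.1: "Where missing data is due to a missed visit values will not be imputed". SAP 7.0, on the main report written once Cohorts 1 and 2 have completed Week 48: "This CSR will include all available data from these two cohorts (including extension data").

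**The concern.** A boy without a result at a visit cannot appear in a normal, abnormal or function-lost row, yet he stays in the denominator. The percentages therefore fall as follow-up becomes incomplete, whatever is happening to the boys who are assessed. Loss of ambulation and cardiac abnormality are outcomes where understatement flatters an uncontrolled, open-label treatment, and a rising rate could print as a falling one.

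The SAP treats continuous data differently. SAP 9.1 pairs each visit mean with the baseline of the subjects who have data at that visit. The categorical rule has no equivalent.

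**Working it through.** **Inputs from the documents.** N = 30 + 10 = 40 planned in Cohorts 1 and 2 (SAP 3.1). In the extension, efficacy tests, leg MRI/MRS, ECG and echocardiogram are six-monthly (SAP 5.2, 5.3.1, 5.4.4, 5.4.5), and physical examination is at the 24- and 48-week columns of each extension year (protocol Time and Events Table). The relevant visits are therefore Weeks 72 and 96.

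**Assumptions, because the documents give no figures.** The finding rate, the dropout, the ECG split and the enrolment period.

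**No percentage in the plan needs reproducing.** The SAP's own potential-to-reach example does reproduce: with a cut on 1 December 2016, first doses on 15 and 25 June 2016 give Study Days 170 and 160, as SAP 9.2 states.

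**1. The identity.** With k findings among n assessed boys, printed % = k/N = (k/n) × (n/N). The dilution factor is n/N. Reading the study population as each table's own analysis set does not remove it, because a baseline assessment alone is enough for entry.

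**2. Up to Week 48.** Here n/N reflects only dropout and missed tests. A 20% rate prints as 19%, 18% or 16% with 5%, 10% or 20% missing.

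**3. ECG time points, Cohorts 1 and 2, Day 1 and Weeks 24 and 48.** SAP 5.4.4 gives each boy either the morning or the evening series. If a share s has the morning series, morning percentages are multiplied by s and evening ones by 1 − s, even with complete data. At s = 0.25, 0.50 and 0.75, a 20% rate at a morning time point prints as 5%, 10% and 15%. For biopsies (9.7.3) the SAP says that a boy not due at a visit is not counted as missing. It has no such sentence for this ECG split.

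**4. Extension visits in the main report.** With even enrolment over E weeks and a cut at the last boy's Week 48, the share with the potential to reach Week W is (E − (W − 48))/E, or zero if that is negative. Printed value of a 20% rate, if every boy who could have reached the visit is assessed:

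| E (assumed) | Share at Week 72 | Prints as | Share at Week 96 | Prints as |
|---|---|---|---|---|
| 26 weeks | 2/26 = 7.7% | 1.5% | 0 | no data |
| 52 weeks | 28/52 = 53.8% | 10.8% | 4/52 = 7.7% | 1.5% |
| 78 weeks | 54/78 = 69.2% | 13.8% | 30/78 = 38.5% | 7.7% |

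**5. Where the boy who has not reached the visit goes.** He is in the denominator, in no category row, and by the 9.1 rule in no missing count. With E = 52 and N = 40 that is 40 × 24/52 = 18.5, so 18 or 19 boys at Week 72.

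**6. Direction of trend.** Take assumed counts of 9/36, 7/20 and 5/10 at successive visits. The rate among assessed boys rises: 25.0%, 35.0%, 50.0%. The printed values are 9/40, 7/40 and 5/40, which fall: 22.5%, 17.5%, 12.5%.

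**7. Attendance.** Assume 90% of the boys who could have reached a visit attend. With 40, 30, 20 and 10 such boys, the ITT denominator prints 36/40 = 90.0%, 27/40 = 67.5%, 18/40 = 45.0% and 9/40 = 22.5%. Divided by the number with potential, it is 90.0% each time.

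**The case against.** The best defence is that this is a display convention. Missing counts are required for categorical as well as continuous variables and are split by cause. Shift tables carry marginal totals, all data are listed, and 9.2 prints the number with potential beside attended and missed. A reader can recompute the rates. Dividing only by assessed boys also has a cost: it invites the assumption that the unassessed resemble them. The default yields to table-level notes, and the TFL list cited in 7.0 is not among the documents.

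Much of this stands, and it limits what can be claimed. A reader might infer any of the following, and the documents do not support them:

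- **That every boy without data is silently counted as free of the finding.** Those who could have reached the visit are shown as missing. Only those who have not reached it are in no row.
- **That the named tables are also diluted at Weeks 60 and 84.** They are not produced there. Vital signs and laboratory tests are collected, but vital-sign categories are cumulative and the by-visit laboratory classification is described as a number.
- **That ECG percentages are halved throughout.** The split affects only the three visits in step 3, and an even split is an assumption.
- **That attendance should be divided by boys with data.** That would give about 100% by construction. Over ITT it is a valid retention rate at any visit every boy could have reached.
- **That the cumulative tables are biased too.** Adverse events and the any-time liver, vital-sign and QTcF criteria are not by-visit percentages, and no harm is shown for them.

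The convention defence fails on one point. Keeping boys in the denominator who could not yet have reached a visit, or who were not due at a time point, is not a cautious treatment of missing data. For unreached visits it also contradicts the rule the SAP applies to its own missing counts.

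**Conclusion.** The point holds as a minor to moderate defect in displayed percentages. That the printed value is the assessed rate times n/N follows from the text. The size rests on assumptions: probably small up to Week 48 apart from the split ECG time points, and material at Weeks 72 and 96, where a 20% rate prints as about 10.8% and 1.5% under even 52-week enrolment. A boy who declines the optional extension would lower those figures further.

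Two things soften it. NSAA and walk tests not done for medical reasons at an attended visit are scored under SAP section 5, so those boys stay in the loss-of-function numerator. The 10% loss of walking distance also has a Kaplan-Meier analysis. No data are lost, and no primary analysis (change in leg MRI/MRS, plasma concentrations, treatment-emergent events) changes, so a reading that the trial's main conclusions are at risk is not supported.

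**What to change.** - **SAP 9.1.** State that by-visit and by-time-point categorical percentages use, as denominator, subjects in the analysis set with a non-missing result, or one imputed under section 5, at that visit or time point. Shift tables use subjects with both a baseline and a visit value. Keep n and the missing counts in every table.
- **SAP 9.2.** Divide attended, missed, discontinued and withdrawn by the number with the potential to reach the visit, which the section already derives.
- **Leave alone.** The denominators of the any-time tables.

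The cost is two or three sentences and a denominator change in the table programs, with no new data. The downside is that denominators then vary by visit and each percentage describes only the boys assessed, which is why the n and missing rows must stay.

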9.1.1 Methods for Handling Dropouts and Missing Data

Imputation details concerning missing efficacy data where a subject has attended the relevant visit are discussed in **Section 5**. Where missing data is due to a missed visit values will not be imputed.

The imputation approaches for handling partial or missing start and/or end dates of AEs and concomitant medications are summarized in **Appendix 2**. Partial and missing AE or concomitant medication dates will be imputed with conservatism. Unless an AE is proven to occur prior to the first dose of the study drug, it will be considered to be a treatment-emergent adverse event (TEAE). Similarly, a medication with a missing stop date will be considered as concomitant medication unless there is obvious evidence that the stop date is prior to the first date of IMP treatment. If the day, or month and day, of the start date are not obviously before the date of first IMP treatment, then the start date will be imputed as the first day of the available month and or year, or the start date of IMP, whichever is later.

The imputed dates will be used to assess whether AEs should be considered to be treatment emergent, medications should be included in the safety summaries as prior and/or concomitant, and for the calculation of AE durations; however, the original partial/missing dates will be included in data listings.

Partial dates for age at diagnosis will also have the missing information imputed for the purposes of calculating the duration since diagnosis. The earliest date consistent with the information provided will be used.

9.1.2 Multiplicity

There will be no multiplicity adjustments for this study.

9.1.3 Pooling of Sites

All sites will be pooled together for the analyses.

9.2 Subject Disposition

The following disposition information will be tabulated:

- Number of subjects screened
- Number (%) of subjects who failed screening, along with reasons for failure
- Number (%) of subjects treated with study drug

- Number (%) of subjects who discontinued study treatment permanently before Weeks 24 and 48, along with reasons for discontinuing
- Number (%) of subjects who completed study treatment (*i.e. not identified as discontinuing study treatment*). This information will be split into two categories, those who complete the study treatment till the study itself closes and those who complete the study treatment till their Week 48 visit and decide not to enter the extension phase.
- Number (%) of subjects who withdrew from the study before Weeks 24 and 48, along with reasons for withdrawal
- Number (%) of subjects who completed the study (*including the end of study visit or approval/discontinuation visit*). This information will be split into two categories, those who complete the study till the study itself closes and those who complete the study till their Week 48 visit, decide not to enter the extension phase and have their follow-up visit (Week 52).
- Number (%) of subjects in each analysis population

Where percentages are presented the number of subjects treated will be used as the denominator, except for the number of subjects who failed screening, where the number screened will be used for the denominator.

If the study isn't terminated prior to Week 48 the study will continue until either SMT C1100 is approved in the relevant countries or development of SMT C1100 is discontinued. For this reason the discontinuation reason 'study terminated by sponsor' will no longer be suitable as this will be the natural closure for the study.

The following will be presented for each scheduled visit:

- Number (%) of subjects who had the potential to reach the visit
- Number (%) of subjects who attended the visit
- Number (%) of subjects who discontinued treatment permanently prior to the visit
- Number (%) of subjects who withdrew from the study permanently prior to the visit
- Number (%) of subjects who missed the visit
- Number (%) of subjects who did not enter extension phase (only applicable for extension visits)

The potential for a subject to have reached a visit will be determined by calculating the duration between the data cut date and the subject's first dose date (*i.e. data cut date – first dose date + 1*), regardless of whether they withdraw from the study. If this duration is longer than the target study day for a visit, then the subject will be deemed to have had the potential to reach the visit. A check will also be made for subject's attending a visit earlier than the visit target day; if this is the case the subject will be included in the count of potential subjects.

For example, consider a data cut date of 1st December 2016

Subject X: has their first dose on 15th June 2016: the data cut date would be the subject's Study Day 170. Hence the subject could have reached the Week 24 visit (168 days).

Subject Y: has their first dose on 25th June 2016: the data cut date would be the subject's Study Day 160. Hence the subject was not scheduled to have reached the Week 24 visit. However, if they attended their Week 24 visit early (*e.g. Day 158*) they would be counted.

For percentages the number of subjects in the ITT/Safety populations will be used as the denominator.

